18.1.11.6 List of deaths

Death can be identified by outcome of AE equal “fatal”.

18.1.11.7 Time to onset of AE

Time to onset will be calculated based on first administration of IMP. Time to onset of AE will be calculated based on the imputed value for AE start date. In case the time of first administration of IMP is missing, time equal “00:00” will be used for calculation.

18.1.11.8 Duration of AE

Duration of AE will be calculated based on the imputed values for AE start date and stop date.

If duration of AE could not be calculated due to unknown date information the following assessment to categories will be used:

- If the AE is marked as “ongoing” the duration will be categorized as “ongoing”
- Otherwise the duration category will be set to “missing”.

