Summary statistics

Data collected in this trial will be summarized according to their nature as follows:

- Continuous variables: number of non-missing observations, arithmetic mean, standard deviation (SD), minimum and maximum values, median and quartiles. If there are less than 5 observations descriptive statistics will be presented based on the rules specified in Section 18.1.2.2.
- Categorical variables: absolute and relative frequencies. If not defined otherwise, the percentage denominator will be the number of subjects in the trial at the respective time point in the analyzed population.

- Time-to-event variables: Kaplan-Meier estimates together with the 95% confidence intervals (CI) will be provided with the respective number at risk and the number censored at the relevant time points. In addition, the median time-to-event and its 95% confidence interval for all arms will be presented. For calculating the survival estimate CI bounds, the log-log transformed estimate of CI bounds will be used. Censoring mechanisms depend on the specific endpoint and will be described in the respective section.

Details on rounding and presentation in case of missing data can be found in Section [18.1.2](#).

Coding of eCRF-entries

All Medication and additional therapies/treatments will be coded using the World Health Organization Drug Dictionary (WHO-DD) or in case of non-medicinal therapies via Medical Dictionary for Regulatory Activities (MedDRA). The versions of these reference documents will be specified on the appropriate statistical outputs.

All investigator-reported terms for medical history in the electronic case report form (eCRF) and all original terms used by the investigators in the eCRFs to identify adverse events (AEs) will be coded using the Medical Dictionary for Regulatory Activities (MedDRA).

For the final analyses, the latest version of the WHO-DD/MedDRA at the time of coding for final evaluations will be used. These might be different for the final analyses of Part 1 and the final analysis of Part 2. Coding for the DMC analyses is addressed in the DMC SAP.

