- Pre-treatment (Part 1 only, all enrolled subjects, by treatment arm and overall)
 - Non-TEAE.
 - Serious non-TEAE.
- Post-treatment (all trial Periods together, SAF, presenting the arms of the Observation Period)
 - Non-TEAE.
 - Serious non-TEAE.

Percentages will be calculated related to the total number of subjects/events presented in the respective table as outlined above for the TEAE tables by SOC and PT.

Analysis by System Organ Class, Preferred Term and descriptors

For Part 1 and the Tapentadol Period of Part 2, the number and percentage of events will be summarized by SOC and PT (sorted alphabetically) for the following AE descriptors. Presentations will be for TEAEs only.

- Intensity: mild, moderate, severe.
- Causal relationship to the IMP: related (with subcategories: possible, probable/likely, certain), not related (with subcategories: not related, unlikely), unknown (with subcategories: conditional/unclassified, assessable/unclassifiable, causal relationship missing).
- Outcome: recovered/resolved, recovering/resolving, not recovered/not resolved, recovered/resolved with sequelae, fatal, unknown.
- Non IMP related countermeasures: none, newly started medication, trial discontinuation, others.
- Action taken with IMP: dose increased, dose reduced, drug interrupted, drug withdrawn, dose not changed, not applicable, unknown.
- Measures of location and variation will be calculated for:
- Duration of TEAEs: Duration will be analyzed in days with measures of dispersion and variation.
- Time to onset of TEAE will be analyzed in days with measures of dispersion and variation.

Denominator for percentage calculation will be the number of all TEAEs for presentation over all SOCs, and the number of TEAEs per SOC or PT respectively for the presentation per SOC and PT, respectively.

The number and percentage of all post-treatment non-TEAEs (all Periods together) will be summarized by SOC and PT (sorted alphabetically) for the following AE descriptors:

- Intensity.
- Time to onset of post-treatment non-TEAEs after last IMP administration will be summarized with measures of dispersion and variation.

Listings

The following listings will be produced for all enrolled subjects:

- Deaths.
- Serious adverse events other than death.
- AEs leading to discontinuation from the trial.
- AEs leading to discontinuation from IMP.
- AEs leading to IMP dose decrease or interruption of IMP.

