18.1.11.1 Handling of missing date information

The term missing date refers to a completely missing date, or to an incomplete date where parts are not available.

Missing start and end date will be imputed conservatively, i.e., missing values will be imputed in such a way that the duration of the AE is considered with the longest possible duration and such that, whenever the AE may potentially start after first IMP administration, the AE will be handled as a TEAE.

I1-I4: imputation steps,
C1-C4: checkpoints

Figure 2: Graphical overview about the imputation strategy

Further explanations on the flow chart: The different steps of the displayed imputation strategy must be completed from the first to the last step. All procedures in each step must be completed in the order given.

- Imputation:

- I1: impute with date of first IMP.
- I2:
Impute with first calendar day and/or first calendar month.
Imputation will be done based on the available partial information starting with month and then day. The respective first month and day will be chosen for imputation:

Missing date	Imputed date
2014-Mar	2014-Mar-01
2014	2014-Jan-01

- I3: Impute with date of informed consent signed
- I4:
Impute with last calendar day and /or calendar last month
Imputation will be done based on the available partial information starting with month and then day. The respective last month and day will be chosen for imputation:

Missing date	Imputed data
2014-Mar	2014-Mar-31
2014	2014-Dec-31

For February leap years must to be taken into account when calculating the last day in February.

- Checkpoints
 - C1: The decision must to be taken based on the available information (date) before imputation.
 - C2: AE stop date before first IMP
 - 1) The decision must to be taken based on the available information (date) before imputation.
 - 2) If the end date is completely missing (with or without the information that the AE was ongoing) this will be considered as after first IMP.
 - 3) If no IMP was given this will be treated as AE stop date before first IMP.
 - C3: The decision must to be taken based on the available information (date) before imputation.
 - C4: The decision must to be taken based on the available information (date) before imputation.

A replacement of missing year for AE start information is not foreseen. If needed this will be considered on a case-by-case decision which must be documented together with the documentation of ADaM data sets.

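### Adverse event duration is summarised only over events with a stop date, with no method for ongoing events, so the reported mean and median are biased downward

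*SAP*

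**What the plan says.** SAP 18.1.11.8 sets the basis of the number: "Duration of AE will be calculated based on the imputed values for AE start date and stop date". For events where this fails it gives two categories, introduced by: "If duration of AE could not be calculated due to unknown date information the following assessment to categories will be used". The first is "If the AE is marked as “ongoing” the duration will be categorized as “ongoing"; anything else becomes missing.

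SAP 18.1.11.1 says how incomplete dates are filled: "missing values will be imputed in such a way that the duration of the AE is considered with the longest possible duration". The written calendar steps work from a partial date (a known year, or year and month). None of them fills a stop date that is completely absent.

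SAP 15.1.2.2, under the analysis by descriptors, gives the summary: "Duration of TEAEs: Duration will be analyzed in days with measures of dispersion and variation". SAP 8.1 says what a continuous summary contains: "Continuous variables: number of non-missing observations, arithmetic mean, standard deviation (SD), minimum and maximum values, median and quartiles". The same section sets a method for censored data: "Time-to-event variables: Kaplan-Meier estimates together with the 95% confidence intervals (CI) will be provided". The SAP uses that method for time to IMP discontinuation (10.2) and time to first rescue intake (13.3.2), but not for event duration.

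**The concern.** An ongoing event drops out of the numeric summary because it outlasted observation. That is selection on the quantity being measured: the longer an event lasts, the more likely it is to be open at the last contact or data cut. The mean and median of the remaining events therefore lie below the true values.

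This runs against two choices made elsewhere in the SAP. Section 18.1.11.1 stretches incomplete dates to the longest possible duration, whereas dropping ongoing events shortens the summary. Section 15.1.2.3 adds exposure-adjusted rates because early discontinuation makes crude incidence hard to interpret, but duration gets no corresponding adjustment.

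What is at stake is a descriptive safety summary in a trial whose Part 2 objective is long-term safety. SAP 6.1 plans a Part 2 interim analysis from a snapshot taken while some children have had little more than 12 weeks of Part 2. A persistent event could look shorter in that first report than in the final one purely because of the cut-off.

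**Working it through.** The plan states no duration, no share of ongoing events and no bias, so there is no figure to reproduce. The check has two steps.

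**1. Follow one event through the rules.** Take an event marked ongoing with no stop date. The written steps of 18.1.11.1 supply no stop date, so 18.1.11.8 gives it the category ongoing. The summary in 15.1.2.2, built as in 8.1 from non-missing values, has no number from it. The numeric set is therefore every event with a known or imputable stop date. The imputation flow chart (Figure 2) is not visible in the text available here, so this rests on the written steps.

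**2. Size under stated assumptions.** Let duration be exponential with true mean m. Let onset be uniform over a window of W days, with cut-off at day F and a = F − W.

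- Share ongoing: P = (m/W)·[exp(−a/m) − exp(−F/m)]
- Loss term: E = (m/W)·[(a + 2m)·exp(−a/m) − (F + 2m)·exp(−F/m)]
- Mean of events with a stop date: R = (m − E)/(1 − P)

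The cut-offs and windows come from the visit schedule; m is assumed. F = 372 is 365 days plus the 7 days to Visit F7D. W = 365 spreads onset over the year. W = 87 is 12 weeks (84 days) plus the 3-day therapeutic reach of SAP 8.2.2. F = 91 with W = 84 represents a child with 13 weeks of follow-up at the snapshot.

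Example with m = 60, F = 372, W = 365, a = 7. The exponentials are exp(−7/60) = 0.8899 and exp(−372/60) = 0.0020.

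- P = (60/365)·(0.8899 − 0.0020) = 0.146
- E = (60/365)·(127·0.8899 − 492·0.0020) = 18.4
- R = (60 − 18.4)/(1 − 0.146) = 48.7 days, which is −19%

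| F | W | True mean | Ongoing | Mean of events with a stop date | Bias |
|---|---|---|---|---|---|
| 372 | 365 | 14 | 2.3% | 13.5 | −4% |
| 372 | 365 | 60 | 14.6% | 48.7 | −19% |
| 372 | 365 | 90 | 22.4% | 63.8 | −29% |
| 372 | 87 | 60 | 0.5% | 58.5 | −2% |
| 372 | 87 | 90 | 2.7% | 81.1 | −10% |
| 91 | 84 | 30 | 26.6% | 18.6 | −38% |

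The median is also biased. By simulation, for a true mean of 90 days (true median 62.4), the median of events with a stop date is about 47 days with onset over the year and about 60 days with onset within 12 weeks.

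The distribution matters. In a simulation with log-normal durations (log-SD 1.5), day-372 cut-off and onset over the year, a true mean of 60 days gives a mean of 31.1 days, or 0.52 of the truth. The median is less affected, at 0.81.

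**The case against.** The strongest case on the other side is about size and reach, and much of it stands.

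- **Early stoppers.** A reader might infer that children who stop tapentadol early have their events cut short. The documents do not support this. These children are meant to move to the Observation Period on the same trial-day count until F12M (Protocol 11.1.4). Adverse events are recorded to last contact (Protocol 12.6.1), and the end date is recorded once per event and not cut at period end (SAP 18.1.11.4). Their events start early and then have time to close.
- **Onset over the year.** The larger 12-month figures need treatment to continue all year. Protocol 8.4 cites a similarly designed trial in which few subjects stayed on medication beyond 1 month, and SAP 7.2.1 names no further need for opioids as a main reason for stopping in Part 2. A short onset window fits this better and gives the smaller figures.
- **Secondary endpoint.** A reader might infer that a main secondary endpoint is biased. SAP 15.1 defines it by number and type of events; duration is one descriptor.
- **Longest events.** A reader might infer that only resolved events count and the longest are always lost. In fact long events that end before last contact are included, some short late-onset events are excluded, and partial stop dates are stretched.
- **Visibility.** Ongoing events are not hidden. They have a category, outcome is tabulated, and carry-over between periods is counted (SAP 15.1.2.1 and 15.1.2.2).
- **Snapshot.** The −38% applies only to the newest children; others at the interim will have longer follow-up, and a final Part 2 analysis follows.

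These points limit the effect but do not remove it. Counting ongoing events does not correct a mean or median computed without them.

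**Conclusion.** The point holds as a modest defect in a descriptive safety summary. As written, the mean and median duration cover only events with a known or imputable stop date, and they are biased downward. The bias mainly affects the Part 2 interim snapshot, children who leave the trial altogether, and events still open at the end of the trial. Stopping IMP while continuing in the Observation Period does not in itself cause it.

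The size is not known from the documents. Under exponential durations and a day-372 cut-off it is about −2% to −19% for a true mean of 60 days and −10% to −29% for 90 days, depending on whether onset falls within 12 weeks or over the year. For events with a mean of two weeks it is about −4% even with onset over the year. Thirteen weeks of follow-up gives about −38% for a true mean of 30 days. Heavier-tailed durations would give more bias in the mean. The primary analysis and the incidence tables are unaffected.

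**What to change.** In SAP 15.1.2.2 and 18.1.11.8:

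1. Label the numeric duration summary as covering events with a stop date, and print the number ongoing beside it.
2. Add Kaplan-Meier median and quartiles of time to resolution, by the method of SAP 8.1, overall and for SOCs and PTs with enough events. Censor ongoing events at last contact or, at the interim, at the snapshot date.
3. For sparse terms, list individual durations with a plus sign for ongoing events.

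The cost is SAP wording and a procedure already in the plan; start dates, end dates and continuing status are already collected. The downside is that with 69 subjects planned the median will not be estimable for some terms, which is why the listing is needed. Censoring at last contact also assumes that leaving the trial is unrelated to how long the event would have lasted, and the table should say so.

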18.1.12 Laboratory, vital signs and ECG parameters

Age determined at Visit V2/VE for Part 1/Part 2, respectively will be used for all reference ranges throughout the trial.

Ordering of parameters

Laboratory parameters, vital signs and ECG parameters will be ordered alphabetically within their parameter group (e.g., hematology, clinical chemistry, and urinalysis). Visits will be sorted chronologically. If changes from BL are displayed by visit all visits will be displayed first followed by all the changes from baseline.

Not exact values

Not exact laboratory values such as < x, > x will not be included in the analysis of continuous parameters. The frequency of occurrence of not exact values will be displayed in the respective table where applicable.

Categorical parameters

For categorical parameters, 2 types of tables are created:

1. Frequency tables display the pre-defined categories by visit and overall post-baseline.
2. Shift tables display the shift from baseline at each visit and overall.

Both types of tables show the number of subjects still in the trial (n) at the visit and the number of missing values (nMiss) at the visit. For the overall presentation, all post-baseline values on treatment are taken into account and nMiss is the number of subjects without any on-treatment post-baseline values.

In tables where parameters are classified as abnormal low, normal, abnormal high based on reference ranges, and alert low, normal, alert high based on sponsor-defined alert ranges the available pre-defined categories must be displayed in tables even if there are categories to which no subjects belong. Categories that are not applicable must be omitted.

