8.2.2 Further definitions

Term	Part/Period	Definition
Pre-treatment-period	-	Before first IMP administration (excluded)
Therapeutic reach	-	
The therapeutic reach is the time after the last IMP intake that a subject is still considered to be potentially affected by a study drug.
 
For tapentadol PR and morphine PR, the therapeutic reach is defined as 72 hours after (last) IMP intake.

On-treatment-period	Part 1	
 • Subjects continuing in the Tapentadol Period after the Treatment Period: 
 a. Start: First IMP administration of Part 1 (included) b. End: 
 i. If the last administration of IMP during Part 1 is more than 3 days before Visit VE: Last administration of IMP during Part 1 + 72 hours (included, therapeutic reach) ii. If the last administration of IMP during Part 1 is less than 3 days before Visit VE: Visit VE (included) c. Start: First IMP administration (included) d. End: Last administration of IMP during Part 1 + 72 hours (included)
	Part 2	
Tapentadol Period only:
 
 a. Start: Visit VE (excluded in case VE is included in the on-treatment period of Part 1; included in case VE is not included in the on-treatment period of Part 1) b. End: Last administration of IMP during the Tapentadol Period + 72 hours (included)
Post-treatment-period	-	After last IMP administration drug intake + 72 hours (excluded)
Enrolled subjects	-	Informed consent form signed. If required by local law an assent form signed.
Treated subjects	-	Subjects with at least 1 administration of IMP.
Treatment completers	Part 1	
Subjects who have completed the 14-day Treatment Period.
 
Completion of the 14-day Treatment Period means that a subject performs the End of Treatment Visit (Visit VE) in the allowed window of 15 ± 1 days, i.e., at or later than Day 14, and has the last IMP intake of part 1 no earlier than Day 13 in the evening.

	Part 2	
Subjects who have completed the 12-month Tapentadol Period.
 
Completion of the 12-month Tapentadol Period means that a subject performs the 12-month follow-up visit (F12M) in the window of 365 ± 14 days, i.e., at or later than 351 days after Visit VE, as part of the Tapentadol Period.

Trial completers	Part 1	Subjects who have completed the 14-day Treatment Period and who performed Visit F7D or entered the Tapentadol Period of Part 2.

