11.1 Subject demographics

Subjects demographics are age [years], body mass index (BMI) [kg/m²], sex, race, ethnicity and age group. Age groups will be 6-<12 years and 12-<18 years.

Weight and height will be collected several times during the trial and will be analyzed separately as safety parameters. The assessments of height and weight at the Enrollment Visit (Visit 1) will be used for the calculation of the BMI. For completeness, baseline values of height and weight are tabulated with subject demographics as well.

Age will be collected at visit V1, V2 and VE.

- Age at Visit V2 will be used for subject demographics of both parts.

Date of signing the informed consent/assent form will be included in the subject data listings only.

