15.2.3 Vital signs

Vital signs measured in the trial are respiratory rate, systolic and diastolic blood pressure and pulse rate.

For each parameter of the vital signs, observed values will be summarized by visit. In addition changes from baseline for all post-baseline visits will be summarized.

Shift tables from baseline for the different visits and overall (worst value on treatment, see Section 18.1.12.1 for definition of worst) will be generated for each vital sign parameter for categories low, normal and high, based on the reference ranges, defined by the sponsor, in Table 9.

Furthermore, a summary by visit and overall post-baseline will be provided on the number and percentage of subjects with alert value results. Alert values are abnormally low or abnormally high measurements regarded as potentially clinically important values defined by the sponsor (Table 10). See Section 18.1.12.1 for details regarding the analysis.

For Part 1, graphical presentations over time of the trial for the observed data will be provided (mean and 95% confidence interval), including numbers on the top and the bottom of the plot representing the number of subjects and the frequency of subjects with abnormally high/low values (based on Table 10) by treatment arm and visit.

For the Tapentadol Period, graphical presentations over time of the trial for the observed data will be provided (mean and 95% confidence interval), including numbers on the top and the bottom of the plot representing the number of subjects and the frequency of subjects with abnormally high/low values (based on Table 10) by visit and the two arms of differently pretreated subjects.

A listing of subjects with vital sign results outside the sponsor defined alert ranges will be provided ([Table 10](#)).

All vital signs values will be presented in the subject data listing of the respective part. Values out of normal ranges ([Table 9](#)) will be flagged as H (above the normal range) or L (below the normal range) in the listing. If a value classified as high or low is in addition also out of alert ranges, it will be flagged as H* or L* in the listing.

Table 9: Normal ranges of vital signs

Parameter (unit)	Age class			
	6 - <9 years	9 - <12 years	12 - <16 years	16 - <18 years
Diastolic BP (mmHg)	57-71	60-75	64-78	65-81
Systolic BP (mmHg)	95-110	101-116	108-121	109-127
Heart rate HR (bpm)	74-111	67-103	62-96	58-92
Respiration rate	18-24	16-22	15-21	13-19

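### Part 2 vital signs are judged for up to 12 months by the child's age at Visit VE, so normal ageing shows up as a modest one-way drift in the shift, flag and alert tables

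*SAP*

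**What the plan says.** SAP 18.1.12 sets the rule: "Age determined at Visit V2/VE for Part 1/Part 2, respectively will be used for all reference ranges throughout the trial". SAP 11.1 lists the visits at which age is recorded: "Age will be collected at visit V1, V2 and VE". None of these is later than VE.

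Part 2 runs about a year beyond VE. SAP 8.2.2 defines a Tapentadol Period completer as a subject who "performs the 12-month follow-up visit (F12M) in the window of 365 ± 14 days".

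SAP 15.2.3 gives the vital-sign limits in four age classes: "6 - <9 years 9 - <12 years 12 - <16 years 16 - <18 years". Three of the four parameters in Table 9 read:

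- "Respiration rate 18-24 16-22 15-21 13-19"
- "Heart rate HR (bpm) 74-111 67-103 62-96 58-92"
- "Systolic BP (mmHg) 95-110 101-116 108-121 109-127"

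Diastolic pressure is 57-71, 60-75, 64-78 and 65-81 mmHg. The same section plans "Shift tables from baseline for the different visits and overall" on Table 9, H and L flags on Table 9, and alert-value counts, a listing and H*/L* flags on Table 10. In Table 10 the respiratory limits are below 12 and above 24 in every class column I could read. The pulse limits there (below 74, 67, 62; above 111, 103, 96) are the Table 9 limits.

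**The concern.** A child recorded as 8, 11 or 15 at VE belongs to the next class a year later but is still compared with the younger one. In Table 9 every respiratory and pulse limit falls from class to class and every blood-pressure limit rises, so the errors do not cancel. Take a child aged 8 at VE with a pulse of 70 at F12M. That is inside the 9 to under 12 range (67-103), but it is below 74, so it would be shifted to low and also counted and listed as an alert value. A respiratory rate of 16 or 17 in the same child is normal for 9 to under 12 (16-22) but is tabulated as low (18-24).

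Part 2 exists to describe long-term safety, and Protocol 10.5.3 names respiratory depression and hypotension as concerns with certain concomitant medication. A table that drifts toward low respiratory rate as children grow, and that partly hides low blood pressure and high pulse, is a poor instrument for that purpose. SAP 18.1.12.1 counts every post-baseline assessment in the overall column, so a misclassified value at one visit carries into the summary.

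**Working it through.** The documents give no figure for the share of children who change class, so there is none to reproduce.

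**1. Share in the wrong class.**

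Inputs:
- Class borders at 9, 12 and 16 (SAP Table 9).
- At least 25% of subjects aged 6 to under 12, with no maximum (Protocol Section 8).
- Age under 18 at VE (Protocol 1.3.1).
- Assumption: ages are uniform within each of the two age groups.

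Over one year the borders are crossed by children aged 8, 11 or 15 at VE. That is two of the six single years in the younger group and one of six in the older. With w the younger share and t the years since VE:

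share = t × [w × 2/6 + (1 − w) × 1/6]

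- F12M (t = 1): w = 25%, 0.25 × 0.333 + 0.75 × 0.167 = 20.8%; w = 50%, 25.0%; w = 75%, 29.2%; w = 100%, 33.3%.
- TP3 (day 84, t = 84/365 = 0.230): 4.8% for w = 25% and 5.8% for w = 50%.
- TP6 (day 168, t = 0.460): 9.6% and 11.5%.

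**2. Direction.** Steps between adjacent classes in Table 9:
- respiratory lower limit −2, −1, −2
- pulse lower limit −7, −5, −4
- systolic upper limit +6, +5, +6
- diastolic upper limit +4, +3, +3

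**3. Size (illustration).** Take values as normal. The mean is interpolated by age through the Table 9 mid-ranges, placed at ages 7.5, 10.5, 14 and 17, with the end slopes continued. The SD is the average half-range divided by the normal quantile for an assumed coverage of 50%, 80% or 95%. The documents do not say what coverage the ranges have. One year of ageing then moves the mean by −0.3 to −0.7 (respiratory rate), −1.3 to −2.5 (pulse), +1.2 to +2.0 (systolic) and +0.7 to +1.2 (diastolic).

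All children, w = 25%, 80% coverage:

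| Flag | At VE | F12M, VE age | F12M, updated age | Excess |
|---|---|---|---|---|
| Low respiratory rate | 11.2% | 16.4% | 12.8% | 3.6 |
| Low pulse | 10.4% | 12.7% | 11.2% | 1.5 |
| High systolic | 11.3% | 16.3% | 11.9% | 4.4 |
| High diastolic | 10.2% | 13.0% | 10.7% | 2.3 |

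Hidden side, same setting: low systolic 8.1% with VE age against 9.9% updated; high pulse 8.7% against 10.1%.

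Over coverage 50-95% and w = 25-50%, the excess runs from 0.9 points (low pulse, 95%, w = 25%) to 5.2 points (high systolic, 80%, w = 50%).

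Share of the drift that updating removes, from the table: respiratory 3.6/5.2 = 69%; pulse 1.5/2.3 = 65%; systolic 4.4/5.0 = 88%; diastolic 2.3/2.8 = 82%.

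**The case against.** The strongest case for the SAP's rule is that a shift table needs one yardstick. If the limits change between baseline and follow-up, an unchanged value can shift. A child aged 8 at VE with systolic 98 at both visits goes from normal (95-110) to low (101-116). In the model, among children who cross a border (w = 25%, 80% coverage), low respiratory rate is 17.5% at VE, 24.9% at F12M with VE age and 7.3% with updated age. This stands as a real cost of updating. Across all children, though, updating leaves much less net drift than freezing, and each flag then matches the SAP's own normal range for age.

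Also true: these are descriptive tables with no safety tests (SAP 15), and observed values and changes are summarised without classes. A bare update would leave subjects who turn 18 without a range, because the tables stop below 18. Under uniform ages that is one of six years in the older group: 0.75/6 = 12.5%, or 0.50/6 = 8.3%. One clause closes this gap.

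Several stronger readings are tempting but not supported:

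- False respiratory alerts. A reader might infer these, but the respiratory limits in Table 10 do not vary across the classes shown.
- The same misclassification in laboratory data. SAP 15.2.1 and 18.2 refer to central-laboratory ranges and a separate statement of work; no age classes are given.
- Larger effects, such as 34% low respiratory rate instead of 10%. That places a child who has just turned 9 at the middle of the 9 to under 12 class and overstates one year of ageing.
- No untreated children to compare with. Observation Period subjects have vital signs at OPx and F12M under the same rule, although SAP 18.1.3 excludes comparison between the periods because the populations differ.

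**Conclusion.** The point holds at moderate size. The rule is explicit, its direction follows from the SAP's own tables, and it sits awkwardly beside the age-adjusted height Z-scores planned for Part 2 (SAP 15.2.7).

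The 21-33% at F12M rests on uniform ages within groups and on the younger share lying between 25% and 100%. It applies to vital signs in children actually assessed at F12M, and earlier visits are affected much less. The 1-5 percentage points rest on the interpolated normal model with 25-50% younger children, and I would not extend that range to a mainly younger population.

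Respiratory rate is affected only in the Table 9 shift tables and H/L flags. Pulse is affected there and in the alert tables and listing, and blood-pressure alert limits also vary by class. The laboratory part is conditional on age-dependent ranges. ECG is recorded in Part 1 only (SAP 15.2.2). The primary analysis is not affected, and nothing here bears on clinical management.

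**What to change.** In SAP 18.1.12, classify each Part 2 vital-sign value, and each laboratory value whose range depends on age, by the child's age at that visit:

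- At F12M: recorded VE age + 1 year, which is right for nearly every child given the ±14-day window.
- At earlier visits: recorded VE age + 0.5 + (visit date − VE date)/365.25, or exact age if it is held. SAP 18.1.5.2 already adds 6 months to recorded years for the height Z-score.
- For subjects who turn 18: keep the 16 to under 18 class.
- In the shift tables, footnote or flag children who cross a class border, since some of their shifts will reflect the change of limits.

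The cost is one SAP rule and one derived variable. The main limit is whole-year age. The formula moves all border-year children together at 0.5 × 365.25 = 182.6 days, between TP6 and TP7. Without exact age, tables to TP6 are therefore unchanged, and classification is least accurate around mid-year. The change is to tabulation only.
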